18. See Section 10.2.1 and [Appendix 2](#). Disease evaluation done at screening, near the end of every 2nd cycle (i.e., after day 15 of cycles 2, 4, 6, 8, etc. and prior to dosing for the next cycle), and, for patients who have not experienced progression at end of treatment, every 12 (\pm 2) weeks until progression or initiation of alternate cancer therapies. Disease evaluation is required at end of treatment only if disease progression is not previously documented. If a partial or complete response is noted, a follow-up radiographic assessment must be done no sooner than 28 days later to confirm response. Prior to any intervention (such as surgical resection, palliative radiation or alternate anticancer therapy), every effort should be made to perform a tumor response assessment in order to document progression and/or confirm an objective response.
19. Unless otherwise specified, all study assessments should be performed prior to administration of study treatment and may be performed up to 24 hours prior to treatment administration if assessments remain within the specified visit window. CDX-3379 should be administered first, with a 1-hour observation period before administration of cetuximab. Diarrhea prophylaxis is required in accordance with Section 8.4.1.4
20. Cetuximab will be administered weekly on Days 1, 8, and 15 of each cycle. On Day 1 of each Cycle, cetuximab should be administered approximately 1 hour after the completion of CDX-3379 administration and after collection of the 60 minute post-infusion PK blood sample. As a routine precaution, patients should be observed for at least 1 hour after the end of the cetuximab infusion. See Section 8.4.2 for guidance on cetuximab premedication and diarrhea prophylaxis. See Section 8 for additional details regarding study treatment dosing, precautions, monitoring, and management of toxicity.
21. All concomitant medications will be documented if taken within 28 days prior to Day 1, and either (whichever occurs sooner): a) through the 30-day post-treatment follow-up, or b) initiation of alternate anticancer therapy. In addition, all anticancer surgeries or medications and response to those medications, as well as any concomitant medications required to treat study drug-related serious adverse events (SAEs), should also be recorded throughout the duration of study follow-up. See Section 9 for further guidance.

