12 STATISTICAL CONSIDERATIONS

Detailed methodology for summary and statistical analyses of the data collected in this trial will be documented in a Statistical Analysis Plan (SAP), which will be developed and maintained by Celldex.

The SAP may modify the plans outlined in the protocol; however, any major modifications of the primary endpoint definition and/or its analysis will also be reflected in a protocol amendment.

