12.2 Analysis Endpoints

Primary Endpoint:

- ORR: The percentage of patients who achieve a best response of CR or PR, confirmed according to RECIST 1.1. Best response is recorded between the date of first dose and the date of documented progression per RECIST 1.1 or the date of subsequent anti-cancer treatment, whichever occurs first. For patients without documented progression or subsequent anti-cancer treatment, all available tumor assessments will contribute to the best response assessment.

Secondary Endpoints:

- CBR: The percentage of patients who achieve best response of confirmed CR or PR, or stable disease (SD) for at least 12 weeks. Best response is assessed as described for ORR.
- DOR: The interval from which measurement criteria are first met for CR or PR until the first date that progressive disease is objectively documented or death, whichever occurs first. Patients who have not progressed or died will be censored on the date of last evaluable tumor assessment; patients who did not have any on-study assessments and have not died will be censored on the date of first dose. If a patient receives subsequent anti-cancer treatment before documented progression, then DOR will be censored on the last evaluable tumor assessment on or before the start date of subsequent anti-cancer treatment.
- PFS: The time from start of CDX-3379 to time of progression or death, whichever occurs first. Patients who have not progressed or died will be censored on the date of last evaluable tumor assessment; patients who did not have any on-study assessments and did not die will be censored on the date of first dose. If a patient receives subsequent anti-cancer treatment before documented progression, then PFS will be censored on the last evaluable tumor assessment on or before the start date of subsequent anti-cancer treatment.
- OS: The time from start of CDX-3379 to death. Patients who have not died will be censored on the date of last contact.
- Safety: Safety will be assessed by vital sign measurements, clinical laboratory tests, physical exams, ECGs, and the incidence and severity of adverse events (graded according to NCI CTCAE v 5.0).
- Pharmacokinetics: Noncompartmental PK parameters will be determined using CDX-3379 serum concentration data obtained prior to, at completion of, and one hour after each CDX-3379 administration as well as on days 8 and 15 of the first cycle; and 30 days post-treatment.

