Special notes on evaluation of overall response:

- Missing assessments and inevaluable designation:
 - When no imaging/measurement is done at all at a particular time point, the patient is not evaluable (NE) at that time point.
 - If only a subset of lesion measurements are made at an assessment, usually the case is also considered NE at that time point, unless a convincing argument can be made that the contribution of the individual missing lesion(s) would not change the assigned time point response. This would be most likely to happen in the case of PD. For example, if a patient had a baseline sum of 50mm with three measured lesions and at follow-up only two lesions were assessed, but those gave a sum of 80 mm, the patient will have achieved PD status, regardless of the contribution of the missing lesion.
- 'Symptomatic deterioration': Patients with a global deterioration of health status requiring discontinuation of treatment without objective evidence of disease progression at that time should be reported as 'symptomatic deterioration'. Every effort should be made to document objective progression even after discontinuation of treatment. Symptomatic deterioration is not a descriptor of an objective response: it is a reason for stopping study therapy. The objective response status of such patients is to be determined by evaluation of target and non-target disease as shown in [Table 12](#) and [Table 13](#).
- In some circumstances it may be difficult to distinguish residual disease from normal tissue. When the evaluation of complete response depends upon this determination, it is recommended that the residual lesion be investigated (fine needle aspirate/biopsy) before assigning a status of complete response. FDG-PET may be used to upgrade a response to a CR in a manner similar to a biopsy in cases where a residual radiographic abnormality is thought to represent fibrosis or scarring.
- For equivocal findings of progression (e.g. very small and uncertain new lesions; cystic changes or necrosis in existing lesions), treatment may continue until the next scheduled assessment. If at the next scheduled assessment, progression is confirmed, the date of progression should be the earlier date when progression was suspected.
- Confirmation of response: In the event of complete or partial responses, efforts should be made to obtain a confirmatory scan (no sooner than 28 days later).

Table 12: Overall response: patients with target +/-non-target disease

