- (b) If that is not possible, check if there IS a baseline exam by the same technique which was used to follow patients...in which case if you retrieve the baseline measures from that technique you retrieve the lesion evaluability
- (c) If neither (a) nor (b) is possible then it is a judgement call about whether you delete the lesion from all forms or consider the impact of the lesion overall is so important that its being non-evaluable makes the overall response interpretation inevaluable without it. Such a decision should be discussed in a review panel.

It is NOT recommended that the lesion be included in baseline sums and then excluded from follow-up sums since this biases in favor of a response.

What if a single non-target lesion cannot be reviewed, for whatever reason; does this negate the overall assessment?

Sometimes the major contribution of a single non-target lesion may be in the setting of CR having otherwise been achieved: failure to examine one non-target in that setting will leave you unable to claim CR. It is also possible that the non-target lesion has undergone such substantial progression that it would override the target disease and render patient PD. However, this is very unlikely, especially if the rest of the measurable disease is stable or responding.

A patient has a 32% decrease in sum cycle 2, a 28% decrease cycle 4 and a 33% decrease cycle 6. Does confirmation of PR have to take place in sequential scans or is a case like this confirmed PR?

It is not infrequent that tumor shrinkage hovers around the 30% mark. In this case, most would consider PR to have been confirmed looking at this overall case. Had there been two or three non-PR observations between the two time point PR responses, the most conservative approach would be to consider this case SD.

A patient has a lesion measurable by clinical exam and by CT scan. Which should be followed?

CT scan. Always follow by imaging if that option exists since it can be reviewed and verified.

A lesion which was solid at baseline has become necrotic in the center. How should this be measured?

The longest diameter of the entire lesion should be followed. Eventually, necrotic lesions which are responding to treatment decrease in size. In reporting the results of trials, you may wish to report on this phenomenon if it is seen frequently since some agents (e.g. angiogenesis inhibitors) may produce this effect.

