6.1. Primary efficacy endpoint

The primary efficacy endpoint of this study is ORR, defined as the percentage of patients who achieve a best response of CR or PR, confirmed according to RECIST 1.1. That is, the criteria for response (CR or PR) must be met again at the next scheduled tumor assessment no sooner than 28 days after the initial documentation. Best response is recorded between the date of first dose and the date of documented progression per RECIST 1.1 or the date of subsequent anti-cancer treatment, whichever occurs first. Anti-cancer treatment includes (a) systemic anti-cancer therapy or (b) radiation or surgical resection of a target or non-target lesion. All anti-cancer treatments will be reviewed and confirmed by the Celldex medical team. For patients without documented progression or subsequent anti-cancer treatment, all available tumor assessments will contribute to the best response assessment.

The number and percentage of patients in each category of BOR (CR, PR, SD, PD, or not evaluable [NE]) will be summarized for the all treated population. ORR will be calculated as defined above, and the corresponding two-sided 95% exact CI will be calculated using the Clopper-Pearson method.

A waterfall plot showing the maximum change from the baseline sum of the diameters of target lesions will be produced for the response-evaluable population. Subgroup waterfall plots may be produced.

A swimmer plot will be produced to present individual patient's tumor response and duration of response over time.

A spider plot will be produced to present change in an individual patient's tumor size with tumor size relative to baseline plotted against month from baseline scan; new lesion and end of treatment dates will be annotated in the plot. Subgroup spider plots may be produced.

Change from baseline in tumor size will be calculated as: Sum of diameters at Week X (mm) – Sum of diameters at Baseline (mm). Percent change from baseline in tumor size will be calculated as: (Sum of diameters at Week X (mm) – Sum of diameters at Baseline (mm)) / Sum of diameters at Baseline (mm) * 100%.

All primary and secondary efficacy outcomes (BOR, DOR if applicable, date of PD if applicable, PFS status, and OS status) will be presented in a single by-patient listing. Individual timepoint assessment data for each lesion will be presented in a separate listing.

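### SAP 6.1 ties confirmation of response to the next scheduled scan, while the protocol and other parts of the SAP ask only for a scan at least 28 days later

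*SAP*

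**What the plan says.** The primary endpoint in Protocol 12.2 is "The percentage of patients who achieve a best response of CR or PR, confirmed according to RECIST 1.1", and SAP 6.1 opens with the same definition. The documents differ on what confirmation means.

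- **SAP 6.1** explains that the criteria for CR or PR "must be met again at the next scheduled tumor assessment no sooner than 28 days after the initial documentation".
- **Protocol Table 1, note 18** says that once a response is noted, "a follow-up radiographic assessment must be done no sooner than 28 days later to confirm response". Protocol Appendix 2, under confirmation of response, gives the same minimum interval as something to aim for. Neither mentions the routine schedule.
- **SAP Exhibit 4, note 18, and SAP 10.3.3** repeat the plain 28-day wording. The opening of SAP Section 6 derives best overall response from the timepoint responses under RECIST 1.1.
- **SAP Exhibit 12** derives best response from pairs of time points. PR followed by PR gives PR, and PR followed by SD gives SD.
- **Protocol Appendix 2, FAQ**, takes this case: "A patient has a 32% decrease in sum cycle 2, a 28% decrease cycle 4 and a 33% decrease cycle 6". It answers that "most would consider PR to have been confirmed looking at this overall case". The SAP's RECIST appendix does not carry the FAQ over.

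On precedence, the SAP's Introduction says its methods prevail where the analyses differ. Protocol 12 lets the SAP modify the planned analyses, but adds that "any major modifications of the primary endpoint definition and/or its analysis will also be reflected in a protocol amendment".

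**The concern.** Whether a patient counts as a responder should not depend on which section the programmer follows. Sites are told to obtain a confirming scan from day 28 onward, and routine scans come about every 42 days. A site that follows note 18 promptly can therefore produce a valid confirming scan between two scheduled ones. SAP 6.1, read literally, sets that scan aside and looks only at the next routine scan.

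This affects the primary endpoint. It also carries through to CBR, to time to response, and to the duration-of-response estimand in SAP 10.1, whose target population is patients with confirmed response. Responder counts will be small, so one reclassified patient visibly shifts the estimate and its lower limit.

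**Working it through.** **1. The timeline.** Routine scans are about every 6 weeks (Protocol 7.1), so at about weeks 6 and 12. Take PR at week 6, PR on a confirmatory scan at week 10, and PD at week 12.

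- Interval from first PR to the confirming scan: (10 − 6) × 7 = 28 days, which meets the minimum.
- Interval from first PR to the next scheduled scan: (12 − 6) × 7 = 42 days.
- The week-10 scan precedes progression, so it falls inside the period in which both documents record best response.
- Under the 28-day wording, and under Exhibit 12 if week 10 counts as a time point, PR then PR gives a confirmed PR.
- Under SAP 6.1 read literally, the next scheduled scan is week 12 and shows PD, so the PR is unconfirmed. Exhibit 12 then gives SD or PD, depending on its 12-week minimum for SD.

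**2. Reproducing the plan's figures.** The lower Clopper-Pearson limit is the 2.5% quantile of Beta(r, n − r + 1), and the upper limit is the 97.5% quantile of Beta(r + 1, n − r).

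| r/n | Protocol Table 11 | Recomputed |
|---|---|---|
| 9/45 | 9.6 to 34.6 | 9.58 to 34.60 |
| 15/45 | 20.0 to 49.0 | 20.00 to 48.95 |
| 7/15 | 21.3 to 73.4 | 21.27 to 73.41 |

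**3. One patient reclassified.** ORR moves by 1/45 = 2.2 points overall, or by 1/15 = 6.7 points in the FAT1-positive cohort.

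| Cohort | Responders | ORR | Lower 95% limit |
|---|---|---|---|
| All treated | 15/45 | 33.3% | 20.0% |
| All treated | 14/45 | 31.1% | 18.2% |
| FAT1-positive | 7/15 | 46.7% | 21.3% |
| FAT1-positive | 6/15 | 40.0% | 16.3% |

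The 15/45 and 7/15 rows are the ones Table 11 offers for ruling out an ORR below 20%.

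**4. If more than one patient is affected.** The documents give no share, so this is an assumption. Suppose a fraction f of responders under the 28-day rule fail the strict rule, and the true ORR under the 28-day rule is 40%. The working rate becomes 0.40 × (1 − f), and the quantity of interest is P(X ≥ 15 | n = 45).

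| f | Working rate | P(at least 15/45) |
|---|---|---|
| 0 | 40% | 85.7% (Table 11: 86%) |
| 5% | 38% | 78.6% |
| 10% | 36% | 69.7% |
| 20% | 32% | 48.0% |

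**5. The FAQ case.** With a baseline sum of 100, the sums are 68, 72 and 67. At cycle 4 the change from the smallest sum is (72 − 68)/68 = +5.9%, short of the 20% needed for PD. The change from baseline is −28%, short of the 30% needed for PR. Cycle 4 is therefore SD. The protocol's FAQ leans towards confirmed PR. Under SAP 6.1 the cycle-2 PR is not confirmed, although a cycle-6 PR met again at cycle 8 would still count.

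**The case against.** The case for leaving the text alone has several parts.

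- **Operational detail belongs in the SAP.** Both documents define the endpoint as confirmed response under RECIST 1.1, and the SAP's precedence clause settles which rule the analysis uses. This holds between the two documents. It cannot settle a disagreement between SAP 6.1 and the SAP's own Exhibit 4 note 18 and Section 10.3.3.
- **The situation is uncommon.** With 6-week scans, the next routine scan will normally satisfy both texts. The conflict needs an extra scan shortly before a routine one, followed by loss of response at the routine one. A required confirmatory scan might also be read as a scheduled assessment. Both points are fair and limit the likely number of patients, but the second shows that the wording leaves a choice open.
- **The strict rule is conservative.** In an open-label, single-arm trial with investigator-assessed response, a stricter definition is the safer one. This is a real trade-off, and it is why the strict result should still be reported.
- **No decision depends on it.** Protocol 12.3 plans no formal hypothesis testing, and SAP 10.1 calls the primary analysis an estimation analysis. That stands.

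A reader might infer that the protocol accepts PR-SD-PR sequences in general. It does not. The FAQ is guidance about shrinkage close to 30%, and it goes on to say that with two or three intervening non-PR scans the most conservative reading is SD. Exhibit 12 works on pairs of scans and has no three-scan row, so it does not squarely contradict the FAQ either.

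**Conclusion.** The inconsistency is real and affects the primary endpoint. The conflict is between a rule tied to the next scheduled scan in SAP 6.1 and a plain 28-day minimum in the protocol and elsewhere in the SAP. Each affected patient is worth 2.2 points of ORR at n=45 and 6.7 points at n=15. The lower limit falls from 20.0% to 18.2% at 15/45 against 14/45, and from 21.3% to 16.3% at 7/15 against 6/15. The number affected cannot be derived from the documents and may be zero. The 5% to 20% range above is illustrative only.

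The result rests on two readings: that SAP 6.1 means a routine scan when it says scheduled, and that the protocol's 28-day minimum admits a scan between routine visits.

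Two further inferences are not supported. One is that Protocol 12 obliges an amendment. Its sentence covers only major modifications, and the documents do not establish that this detail is one. The other is that moving from 10/45 to 9/45 (lower limit 11.2% to 9.6%) loses the 10% benchmark. Table 11 itself uses 9/45, with its 9.6% limit, as the result for ruling out an ORR below 10%.

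**What to change.** In SAP 6.1, replace the condition on the next scheduled scan with wording such as: *the criteria for CR or PR are met again at a later evaluable tumor assessment, whether scheduled or obtained for confirmation, at least 28 days after response was first documented and before any progression or subsequent anti-cancer treatment.* Report ORR under the strict next-scheduled-scan rule as a sensitivity analysis.

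Separately, state how the single near-threshold PR-SD-PR case in the protocol's FAQ is to be scored, make Exhibit 12 consistent with that statement, and show its effect in the sensitivity analysis. Do not add a general allowance for any intervening SD or NE. The documents contain none, and it would loosen an open-label, investigator-assessed endpoint.

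The cost is a few sentences and one extra derivation, made in a revised SAP before database lock as SAP 4.11 provides. The downside is a slightly less strict primary definition, which the sensitivity analysis makes visible.

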6.2. Secondary efficacy endpoints

6.2.1. Duration of response

DOR is defined as the interval from which measurement criteria are first met for CR or PR until the first date that progressive disease is objectively documented or death, whichever occurs first. Patients who have not progressed or died will be censored on the date of last evaluable tumor assessment; patients who did not have any on-study assessments and have not died will be censored on the date of first dose. If a patient receives subsequent anti-cancer treatment before documented progression, then DOR will be censored on the last evaluable tumor assessment on or before initiation of subsequent anti-cancer treatment. The censoring rules are outlined in Exhibit 6.

DOR will be estimated in the all treated population using the Kaplan-Meier (KM) product limit method and displayed graphically. The KM estimate of the median DOR and the corresponding two-sided 95% CI, calculated using the Brookmeyer and Crowley's method (log-log transformation), will be presented.

Time to response, defined as the time from first dose date to the date of first confirmed response (CR or PR), will also be estimated in the all treated population using the Kaplan-Meier (KM) product limit method. The KM estimate of the median time to response and the corresponding two-sided 95% CI, calculated using the Brookmeyer and Crowley's method (log-log transformation), will be presented alongside DOR.

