10.1. Estimand framework

A summary of the attributes of the primary estimand is provided in Table 1.

Table 1. Estimand attributes for the primary efficacy analysis

Estimand attribute	Description of attribute
Target population	All treated population: All patients treated with CDX-3379.
Primary patient-level variable	Best overall response (BOR) according to RECIST 1.1. Patients can have a BOR of complete response (CR), partial response (PR), stable disease (SD), progressive disease (PD), or unknown.
Handling of intercurrent events	Alternative anti-cancer therapies will be intercurrent events in the determination of BOR. Assessments that occur after the date of documented progression per RECIST 1.1. or the date of anti-cancer treatment, whichever occurs first, will not contribute to the determination of BOR.
Population-level summary	ORR, defined as the percentage of patients who achieve a best response of CR or PR, confirmed according to RECIST 1.1., for all patients treated with CDX-3379 in combination with cetuximab.

The trial product estimand is defined as ORR based on assessments on or prior to the date of PD or data of anti-cancer therapy, whichever occurs first. Patients who discontinue study therapy for reasons other than progression will continue to have tumor assessments until disease progression or initiation of subsequent anti-cancer therapy, whichever occurs first. Therefore, treatment discontinuation is not considered an intercurrent event. The primary efficacy analysis will be an estimation analysis for this estimand (point estimate of ORR and associated 95% confidence interval).

Duration of response is an important secondary analysis because it characterizes ORR. A summary of the attributes of the estimand associated with this important secondary endpoint is provided in Table 2.

Table 2. Estimand attributes for the important secondary efficacy analysis

Estimand attribute	Description of attribute
Target population	All patients treated with CDX-3379 who have a BOR of confirmed CR or PR (objective response).

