Primary patient-level variable	Duration of response is calculated as the date of first CR or PR that is subsequently confirmed to date of documented disease progression or death due to any cause, whichever occurs first. In patients who have objective response and are progression-free and alive at the time of the analysis, duration of response is calculated as the date of first CR or PR that is subsequently confirmed to the date of last evaluable tumor assessment.
Handling of intercurrent events	Alternative anti-cancer therapies may be intercurrent events in the calculation of duration of response. In patients with objective response who receive an anti-cancer therapy prior to documented disease progression, duration of response will be censored on the start date of the anti-cancer therapy.
Population-level summary	A Kaplan-Meier plot will show duration of response in patients who have objective response. The median duration of response will be shown as a population-level summary statistic.

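### SAP 6.2.1 and estimand Table 2 define duration of response differently (whether the response must be confirmed, and the censoring date at new therapy), so the reported median need not describe the responses counted in the ORR

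*SAP*

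**What the plan says.** SAP 6.2.1 sets the start of DOR without mentioning confirmation: "DOR is defined as the interval from which measurement criteria are first met for CR or PR". It then names the analysis set: "DOR will be estimated in the all treated population using the Kaplan-Meier (KM) product limit method and displayed graphically". Its censoring text also covers patients who were never scanned: "patients who did not have any on-study assessments and have not died will be censored on the date of first dose". At new anti-cancer therapy before progression, 6.2.1 and Exhibit 6 censor at the last evaluable assessment on or before that therapy. Protocol 12.2 has the same start, "DOR: The interval from which measurement criteria are first met for CR or PR", and the same censoring.

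SAP Appendix 10.1, Table 2, describes DOR as an important secondary analysis because it characterizes the ORR. Its target population is "All patients treated with CDX-3379 who have a BOR of confirmed CR or PR (objective response"). Its patient-level variable reads "Duration of response is calculated as the date of first CR or PR that is subsequently confirmed to date of documented disease progression" or death, and its summary is "A Kaplan-Meier plot will show duration of response in patients who have objective response". At new therapy, Table 2 censors on the start date of that therapy.

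The ORR in SAP 6.1 counts only confirmed responses. The criteria must be met again at the next scheduled assessment, at least 28 days later.

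**The concern.** A DOR reported beside a confirmed ORR should be the duration of those same responses. As written, 6.2.1 lets in a patient who meets PR once and then progresses. That patient has a date on which criteria were first met, so 6.2.1 gives a duration, usually a short one. SAP Exhibit 12 gives the same patient a best response of SD or PD, so the patient is in neither the ORR numerator nor Table 2.

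Two programmers working from this one SAP could therefore report different medians. Few responders are expected, so a handful of unconfirmed responses can move the median visibly, most of all in the FAT1, FAT1/NOTCH and oral-cavity subgroups. SAP 6.3 sends those subgroups to the methods of 6.1 and 6.2, not to Table 2.

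**Working it through.** The documents state no DOR figure, so there is none to reproduce. The check sets the two rules side by side and then sizes the difference under stated assumptions.

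**Step 1. Compare the rules by response pattern** (scans about every 6 weeks on treatment; SAP 2.1)

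| Pattern | In the ORR (6.1, Exhibit 12)? | DOR under 6.2.1, read literally | DOR under Table 2 |
|---|---|---|---|
| PR week 6, PR week 12 | Yes | Starts week 6 | Starts week 6 |
| PR week 6, PD week 12 | No (SD or PD) | 12 − 6 = 6 weeks | Not included |
| PR week 6, SD week 12, PR weeks 18 and 24 | Yes | Starts week 6 | Starts week 18 under the 6.1 confirmation rule |
| Never a CR or PR | No | No start date | Not included |

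The second row changes who is in the analysis. The third changes the start by 18 − 6 = 12 weeks, but only for an interrupted response. In the ordinary case, the first row, the rules agree.

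**Step 2. Size of the patient-set difference (illustration)**

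Assumptions, none from the documents except where noted:
- c confirmed responders with exponential DOR and median m. The case c = 9 corresponds to the 9/45 row of Protocol Table 11.
- u unconfirmed responders, each progressing at the next 6-week scan: 42 / 30.4375 = 1.38 months (month length from SAP 4.4).
- No censoring.

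After 1.38 months the pooled curve is S(t) = [c/(c+u)] × exp(−ln2 × t/m). Setting S(t) = 0.5 gives median = m × log2[2c/(c+u)], valid when the result exceeds 1.38 months.

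| c | m (months) | u | Calculation | Pooled median (months) |
|---|---|---|---|---|
| 9 | 6.0 | 0 | 6 × log2(18/9) | 6.0 |
| 9 | 6.0 | 1 | 6 × log2(18/10) | 5.1 |
| 9 | 6.0 | 2 | 6 × log2(18/11) | 4.3 |
| 9 | 6.0 | 3 | 6 × log2(18/12) | 3.5 |
| 9 | 4.0 | 2 | 4 × log2(18/11) | 2.8 |
| 9 | 9.0 | 2 | 9 × log2(18/11) | 6.4 |
| 3 | 6.0 | 1 | 6 × log2(6/4) | 3.5 |
| 3 | 6.0 | 2 | 6 × log2(6/5) | 1.6 |

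**Step 3. The no-assessment sentence**

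A patient with no scans has no response date, so no DOR can be calculated. If such a patient were entered anyway as censored at the origin, he or she would leave the risk set before any event. Each Kaplan-Meier factor (1 − d/n) would be unchanged, and only the displayed N would rise.

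**Step 4. Censoring at new therapy**

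Take a response from week 6, a last evaluable scan at week 12 and new therapy at week 16 (hypothetical). Section 6.2.1 censors at 12 − 6 = 6 weeks; Table 2 censors at 16 − 6 = 10 weeks. The gap is the time from last scan to new therapy. With scans on schedule it is up to about 6 weeks on treatment and about 12 (± 2) weeks after stopping without progression. It alters the curve only if another patient's event falls inside it.

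**The case against.** The best reply is that the SAP already shows its intent. Section 6 says the efficacy analyses follow the estimand framework and refers to Appendix 10.1 for details, so Table 2 can be read as the detail behind 6.2.1. On that reading, the all treated population is only the parent set, as opposed to the response-evaluable set; Table 2 itself begins from all treated patients. SAP 6.1 lists DOR only where applicable. Dating from when criteria are first met also serves to exclude the later confirmatory scan date, which agrees with Table 2.

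Much of this stands as evidence of intent, but it does not settle the matter. No text says Table 2 overrides 6.2.1. The SAP's precedence statement in Section 1 ranks SAP over protocol, not one SAP section over another. Within 6.2.1 itself, time to response is tied to a confirmed response and is to be shown beside DOR, while the DOR definition lacks that condition.

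Some stronger readings are tempting and should not be drawn:
- **A reader might infer that non-responders enter the DOR curve.** They have no start date, and the listing wording in 6.1 points the other way.
- **A reader might infer that censoring unscanned patients at first dose biases the median.** It does not (Step 3); it is a leftover that matches the PFS wording.
- **A reader might infer that start dates are generally wrong.** They differ only for interrupted responses. Even then, the question-and-answer part of Protocol Appendix 2 would treat a 32%, 28%, 33% sequence of decreases as a confirmed PR. On that view both rules start at the first PR. The stricter next-assessment rule in SAP 6.1 is what separates them.
- **A reader might infer that the reported DOR is bound to be wrong.** If there are no unconfirmed or interrupted responses and no new therapy before progression, the two rules give the same result.

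**Conclusion.** The inconsistency is real and should be resolved before the analysis. Its main consequence is the patient set: followed literally, 6.2.1 admits unconfirmed responders and shortens the median. In the illustration with 9 confirmed responders and a 6.0-month median, 1 to 3 unconfirmed responders bring it to about 5.1 to 3.5 months; with 3 confirmed responders, a single one brings it to 3.5. These figures rest on the assumptions in Step 2; how many unconfirmed responses will occur is not known from the documents.

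The start-date difference is rarer and acts in the opposite direction, lengthening DOR. The censoring conflict is a separate discrepancy whose effect depends on how many responders start new therapy before progression.

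DOR is a secondary, descriptive endpoint in a single-arm estimation study, and the primary ORR is untouched. The point is a recommended clarification, not a threat to the main result.

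**What to change.** Change the SAP only:

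1. In 6.2.1, state that DOR is estimated among all treated patients with a confirmed CR or PR, from the first CR or PR that is subsequently confirmed under the 6.1 rule. Derive that date from the same time-point responses used for best overall response, not from the separately recorded date of first response mentioned in Section 6.
2. Remove the no-assessment censoring sentence for DOR and limit the third and fourth rows of Exhibit 6 (no baseline assessment; no on-study assessment and no death) to PFS. This is tidying and does not change the Kaplan-Meier estimate.
3. Use one censoring date for subsequent anti-cancer therapy in 6.2.1, Exhibit 6 and Table 2. The last evaluable assessment on or before therapy is the natural choice, since the protocol, 6.2.1 and Exhibit 6 already use it; only Table 2 would change.

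The cost is a few lines of SAP text, with no new data. A protocol amendment is not needed: SAP Section 1 lets the SAP prevail where its analyses differ, and Protocol Section 12 requires an amendment only for major changes to the primary endpoint or its analysis.
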